### **3.8.4.2 Clinical Laboratory Assessments**

Clinical laboratory assessments will be summarized using standard summary statistics for continuous parameters and using frequencies and percentages for categorial parameters. Results will be listed for each subject and flagged high or low relative to the normal range where appropriate. Clinical laboratory test results will be listed in SI units (Metric). Concentration values below the limit of quantification (BLQ) will be analyzed at the lower limit of quantification (LLOQ) when calculating summary statistics.

#### Clinical Chemistry and Hematology

Clinical chemistry and hematology values will be presented at Screening, Baseline, Week 1, Week 2, Week 4, Week 12 and Week 24 (End of Study) or Early Termination. HbA1c will be presented at Screening and at Week 24 (End of Study) or Early Termination visit.

#### Serum Cortisol

Serum cortisol will be presented at Screening, Baseline, Week 1, Week 2, Week 4, Week 8, Week 12, Week 18, and Week 24 (End of Study) or Early Termination.

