1.2.2 Clinical Summary

A Phase 1 study has been conducted in Canada, in 32 subjects with knee OA. Subjects were randomized in a 3:1 ratio to receive either a single IA dose of 15 mg EP-104IAR or vehicle-control (24 subjects received EP-104IAR and 8 subjects received vehicle). Subjects were followed for up to 42 weeks post-dose with safety, efficacy and PK assessments (plasma and synovial fluid).

EP-104IAR was safe and well-tolerated. Treatment-emergent adverse events (TEAEs) occurred in 15 subjects (62%) in the EP-104IAR group (34 events) and in 4 subjects (50%) in the vehicle group (9 events). Subjects most frequently experienced TEAEs of Grade 1 (mild) severity (11 subjects, 46% in the EP-104IAR group versus 4 subjects, 50% in the vehicle group) and most TEAEs were observed within the first 12 weeks of the study (31 out of 43 TEAEs).

There were no deaths, no serious adverse events (SAEs) considered related to EP-104IAR and no TEAEs that led to withdrawal. There were no local safety findings (based on review of TEAEs, physical examination and gait assessments of the treated knee).

Average cortisol levels showed no clinically significant deviations compared to placebo and remained within the normal range of cortisol variation. There was a noticeable decrease in cortisol at 48 hours post-dose in some EP-104IAR subjects. Two subjects showed a transient decrease of >75% from baseline; one of which returned to baseline levels by one week and the other by three weeks.

Plasma PK was predictable, with concentrations within acceptable safety margins (based on marketed FP products). Synovial fluid FP levels were approximately 1- to 2-orders of magnitude higher than plasma levels and at theoretically efficacious concentrations for the majority of subjects.

The median dose of FP delivered in this study was 13.2 mg (approximately 88% of the intended dose).

Study EP-104IAR-101 was primarily a safety and PK study; however, a variety of pre-specified efficacy endpoints were included to permit a preliminary evaluation of the efficacy of EP-104IAR in comparison to vehicle. Pain and OA symptoms were measured using PtPain, WOMAC Index 3.1, and a Patient Global Assessment of Arthritis (PtGA). A Physician's Global Assessment of Arthritis (MDGA) and an evaluation of subjects' overall health status using the Short Form 36 health survey (SF-36) were also collected.

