2.1.2 Dose Justification Based on Systemic Exposure

Data from the prior clinical study (EP-104IAR-101) showed clear and predictable systemic PK. The impact of systemic FP is well understood from knowledge of Flovent HFA (in addition to several other marketed formulations of FP). Established knowledge of systemic FP exposures was used to evaluate systemic safety of EP-104IAR at the 25 mg dose for use in this study.

A PK model was developed using data from Study EP-104IAR-101. Based on this model, average concentrations from a single administration of 25 mg EP-104IAR are expected to peak at around the maximum concentration (C_{max}) from a 440 μ g b.i.d. Flovent HFA dose. They then fall below the C_{max} from a 220 μ g b.i.d. Flovent HFA dose by 1 week post-dose; and below the average concentration at steady state (C_{ss}) from a 220 μ g b.i.d. Flovent HFA dose by 2-3 weeks post-dose. The total exposure to FP over 24 weeks following a single 25 mg dose of EP-104IAR is expected to be the same as receiving an average of approximately 120 μ g b.i.d. Flovent HFA over an equivalent period.

It is known that systemic levels of corticosteroids can impact the hypothalamic-pituitary-adrenal (HPA)-axis. Given the expected systemic PK of EP-104IAR, it is anticipated that some perturbation of endogenous cortisol may occur. Based on the modelled PK data, it is expected that peak cortisol suppression with a 25 mg dose of EP-104IAR will be similar to that seen with Zilretta[®] (an extended-release TCA product approved in the United States), and substantially better than immediate release TCA, but with faster return to baseline levels. In this study, subjects will be closely monitored for signs of adrenal insufficiency, see Section 2.2 below, for details.

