9.2.5.1 Visit 3 (Day 3 ±1 day)

Subjects will attend the site approximately 48 hours following dosing to provide blood samples for hematology, clinical chemistry, cortisol and PK assessments only. Any AEs reported by the subject will be recorded.

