9.2.5.2 Visit 4 (Week 2, Day 15 ±3 days)

The following assessments will be performed at this visit:

- Blood samples for hematology, clinical chemistry, cortisol and PK.
- Vital signs.
- Exam of Index knee.
- Recording of AEs and changes in conmed use.
- Rescue medication accountability will be performed and additional rescue medication provided if necessary.
- Check ePRO device and provide re-training if necessary.

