### **3.9 Analysis of Plasma Pharmacokinetic Concentrations**

The pharmacokinetics of EP-104IAR will be assessed by analysis of plasma levels of fluticasone propionate (FP). Blood samples for determination of FP plasma concentrations will be collected at following time points relative to study drug administration: Pre-Dose, 2 hours Post-Dose, Week 1, Week 2, Week 4, Week 8, Week 12, Week 18 and Week 24 (End of Study). PK data will be analyzed using the Safety Population.

Where estimable, the following plasma PK parameters calculated for FP will be calculated using non-compartmental methods:

- the maximum quantifiable plasma concentration ( $C_{max}$ )
- the time to reach maximum quantifiable plasma concentration ( $t_{max}$ )

	EP-104IAR-201 Statistical Analysis Plan	Version: Final 1.0
	Date: 14-Jun-2023	Page 28 of 38

- the last quantifiable plasma concentration ( $C_{last}$ )
- the time to reach the last quantifiable plasma concentration ( $t_{last}$ )
- the terminal disposition rate constant ( $\lambda_z$ ) with the respective half-life ( $t_{1/2}$ )
- the area under the concentration-time curve from time zero to the time of last quantifiable concentration ( $AUC_{0-t}$ )
- the area under the concentration-time curve from zero to infinity ( $AUC_{0-\infty}$ )
- the area under the concentration-time curve from time zero to 24 weeks post-dose ( $AUC_{0-24wks}$ )
- the percentage of the area under the concentration-time curve extrapolated to infinity ( $AUC\%_{extrap}$ )
- the apparent clearance (CL/F)
- the apparent volume of distribution ( $V_z/F$ ).

The individual PK parameters of FP will be presented in data listings and summarized for subjects receiving EP-104IAR using descriptive statistics (number of subjects, mean, SD, geometric mean, geometric mean CV, median, Q1, Q3, minimum, and maximum). Geometric mean versus nominal time profiles will be presented in figures on both linear and semi-logarithmic scales (base 10). Concentration values that are BLQ of the assay will be treated as half the LLOQ when calculating summary statistics for plasma concentrations. Where all values are BLQ, the mean, geometric mean, median, minimum, and maximum concentration will be presented as BLQ and the SD will be reported as not applicable. Concentration values reported as BLQ will be listed with the LLOQ in parentheses. Missing values will not be imputed when calculating summary statistics for plasma drug concentrations and for calculating PK parameters.

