#### 4.4 Unscheduled Data

Except for ACTH stimulation test results as described below, data obtained from unscheduled assessments (which also includes early exit visits) will only be considered for baseline determination; otherwise, unscheduled data will not be used in summary tables or included in the analyses. All unscheduled data will be presented in the listings.

ACTH stimulation test results will be mapped via the windowing rules in the below table. When more than one result for a subject occurs within one visit window, the worst result (i.e., Fail) will be mapped to that visit.

Visit (Mapped)	Target Day	Study Day Range
Screening		<1
Week 1	Day 3	1-9
Week 2	Day 15	10-22
Week 4	Day 29	23-43
Week 8	Day 57	44-71
Week 12	Day 85	72-106
Week 18	Day 127	107-148
Week 24	Day 169	149+

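### The SAP plans no by-arm count of subjects with marked cortisol suppression, although Phase 1 averages looked unremarkable while two subjects fell by more than 75%

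*SAP*

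**What the plan says.** **Summaries.** SAP 3.8.4.2 (Serum Cortisol) states: "Serum cortisol will be presented at Screening, Baseline, Week 1, Week 2, Week 4", and continues with Weeks 8, 12, 18 and 24 or early termination. SAP 3.8.4 gives continuous safety parameters summary statistics by time point and change from baseline, and adds figures of the cortisol time profile. Shift tables are for categorical parameters. Under SAP 3.1 the standard statistics include the median, quartiles, minimum and maximum. SAP 3.8.4.2 also provides subject listings flagged against the normal range where appropriate, and a frequency and percentage of positive ACTH stimulation tests.

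**Cortisol limits in the protocol.** Section 9.1.5.1.2 uses <350 nmol/L at Week 8 and Week 24 as a trigger for the ACTH test. It uses ≤138 nmol/L at any post-dose visit only when signs and symptoms of adrenal insufficiency are also present.

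**Phase 1.** Protocol 1.2.2 reports no clinically significant deviation in average cortisol, a noticeable fall at 48 hours in some EP-104IAR subjects, and: "Two subjects showed a transient decrease of >75% from baseline". One of these two was back at baseline by one week and the other by three weeks.

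**Timing.** Protocol 9.2.5.1 (Visit 3, Day 3 ±1): "Subjects will attend the site approximately 48 hours following dosing to provide blood samples for hematology, clinical chemistry, cortisol and PK assessments only". The next cortisol sample is at Visit 4, Day 15 ±3 (Protocol 9.2.5.2). SAP 3.9 lists the PK times, relative to dosing, as "Pre-Dose, 2 hours Post-Dose, Week 1, Week 2, Week 4" and onward.

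**The concern.** The adrenal axis is a main systemic safety question here. Protocol 2.1.2 anticipates some perturbation of cortisol, and Protocol 2.2 adds precautions because the dose is higher than in Phase 1. Morning cortisol is the only adrenal measure taken after dosing in every subject.

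If suppression is confined to a minority, means and medians move little and a reader of the tables cannot tell how many subjects were affected or how the arms compare. That comparison needs a vehicle arm: Protocol 6.2 expects natural fluctuation alone to take many subjects in both arms below the ACTH trigger, so only a proportion by arm separates drug effect from background. SAP 3.8.4.1 leaves the final designation of adverse events of special interest until after database lock, so a count defined beforehand carries more weight than one chosen later.

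A smaller matter is the label. The first post-dose cortisol, laboratory and PK sample is called Week 1, and that label has two meanings in the SAP.

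**Working it through.** The plan states no cortisol figure to reproduce. The arm size used below can be checked against SAP 3.3:

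- n per arm = 2 × (1.96 + 0.84)² × 2.2² / 0.8² ≈ 119, against about 120 stated; power at 120 is 0.804.
- 120 / (1 − 0.20) = 150 randomised and dosed per arm.

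**Inputs for the illustration.** Two subjects with a >75% fall and 24 subjects on EP-104IAR (Protocol 1.2.2); 150 treated (SAP 3.3).

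**Assumptions.** Both subjects were on EP-104IAR (the text implies this but does not state it). The Phase 1 rate carries over to this dose. The fall is exactly 75%. Affected subjects start at the arm's average baseline. The other subjects have no average change.

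- Rate: 2/24 = 8.3%; exact (Clopper-Pearson) 95% CI 1.0% to 27.0%.
- Subjects a table would count: 150 × 0.0833 = 12.5 (1.5 to 40.5 over the interval).
- Shift in the arm mean: 0.0833 × (−75%) = −6.25% (−0.8% to −20.3% over the interval). If the affected subjects fell to zero the shift would be 0.0833 × (−100%) = −8.3%, so the answer depends little on how far beyond 75% they fell.
- Simulation of 150 subjects, with an assumed SD of 20, 30 or 40 percentage points in the others: the median moves by about −2% to −4%. Q1 moves from −13, −20 or −27% without suppressed subjects to −18, −27 or −36% with them.
- Probability of at least one such subject among 150: above 0.9999 at 8.3%, and 0.79 at the lower limit.

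The minimum and the listings would therefore very probably show that an extreme fall occurred. No planned table would show whether it was one subject or a dozen, or how the arms differ.

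**Can the ACTH table stand in?** After dosing the test is triggered by <350 nmol/L at Week 8 or Week 24, by ≤138 nmol/L together with signs and symptoms, or by a last value <350 nmol/L in a subject who withdraws early (Protocol 9.1.5.1.2 and 9.2.7). A subject who stays in the trial with low cortisol at 48 hours and no symptoms triggers nothing at that visit.

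**Can the flags?** They are set against the normal range. Protocol 9.1.5.1.2 describes values under 350 nmol/L as at the lower end of that range, so a normal-range flag need not mark them.

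**The label, side by side.**

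| Place | Meaning of Week 1 |
|---|---|
| Protocol Schedule of Events | Day 3 falls under Study Week 1 |
| SAP 4.4, ACTH windows | target Day 3, Days 1–9 |
| SAP 4.1, WOMAC Pain windows | target Day 8, Days 7–13 |
| SAP 3.8.4.2 and 3.9 | not defined; the sample is at Visit 3, Day 3 |

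SAP 3.9 also plans geometric mean concentrations against nominal time, without stating the nominal time for this sample.

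**The case against.** The strongest reply is that individual falls are not lost. Figures, flagged listings, quartiles and the minimum are planned, the Medical Monitor reviews post-dose cortisol, and the safety review committee receives summaries by group and subject listings. Phase 1 did detect and report its two subjects. This stands: a reader might infer that cortisol will be reported only through averages, or that the planned form concealed the signal in Phase 1, and the documents support neither. What is missing is the count. Oversight during the trial does not supply one for the final report.

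The limits can also be challenged. The <350 nmol/L value is meant to be conservative and will be unspecific, the number tested at Week 12 already approximates the Week 8 count below it, and >75% is a Phase 1 description rather than a defined criterion. This stands in part. It is a reason to lead with ≤138 nmol/L and the >75% fall and to footnote <350 nmol/L. It does not supply a count at 48 hours.

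On the label, a reader might infer that the 48-hour sample will be displaced by five days, or that suppression will be read as lasting a week. The documents do not show this. Week 1 is the protocol's own heading for Day 3, SAP 4.1 presents data other than PK and WOMAC on the planned schedule, and PK parameters use actual sampling times. Nor would a low Week 1 cortisol contradict the dose rationale: the statement in Protocol 2.1.2 ("Flovent HFA dose by 1 week post-dose") concerns modelled drug concentration. In Phase 1 one of the two subjects took up to three weeks to recover. With no sample scheduled between Day 3 and Day 15, this design cannot date recovery within that interval.

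**Conclusion.** The point holds as a reporting gap. At the observed Phase 1 rate the arm mean would move about 6%, while about 12 of 150 treated subjects would be counted.

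This rests on two subjects, and the interval is wide. At 27% the mean would move about 20% and would show the effect without a count; at 1% there would be one or two subjects. The dose is also higher (25 mg against a median of 13.2 mg delivered in Phase 1). If the remaining subjects fall as well, the mean moves more and the dilution is less. Dilution is therefore a plausible risk, not a certainty. The documents give no cortisol mean or SD, so the size cannot be stated in nmol/L or standard errors without further assumptions.

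The Week 1 label is a minor ambiguity that affects how tables and nominal-time plots are read. Nothing here touches the primary analysis, the sample size or the error rate.

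**What to change.** In SAP 3.8.4.2 (Serum Cortisol), add one descriptive table for the Safety Population, by arm, by visit and for any post-dose visit, giving n/N (%) with:

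- morning cortisol ≤138 nmol/L;
- a fall of more than 75% from Visit 2;
- morning cortisol <350 nmol/L, with a footnote that Protocol 6.2 expects many subjects in both arms to fall below the testing trigger.

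Use the Visit 2 morning sample as the reference for the fall. Under the general baseline rule in SAP 4.1 a missing Visit 2 value would be replaced by a Screening value, which Protocol 9.1.5.1.1 allows at any time of day. No hypothesis test is needed, and the table implies no change to any clinical rule.

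Label the Visit 3 sample Day 3 (48 h) in the cortisol, laboratory and PK outputs, and plot it at that nominal time.

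The cost is one table and a label change, from data already collected. If the change comes after unblinding, mark the table as post hoc.

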#### ACTH Stimulation Tests

Results for ACTH stimulation tests will be summarized by frequency and percentage of positive tests, and listed for each subject.

#### Urine Pregnancy and Urinalysis Dipstick Tests

Urinalysis dipstick and safety, and urine pregnancy test results will be presented in data listings and the urinalysis drug and safety test results will be summarized in shifts from baseline tables.

### **3.8.4.3 Vital Signs**

	EP-104IAR-201 Statistical Analysis Plan	Version: Final 1.0
	Date: 14-Jun-2023	Page 27 of 38

Vital sign measurements will be summarized at Screening, Baseline and 1-hour post-dose, Week 2, Week 4, Week 8, Week 12, Week 18, and Week 24 (End of Study) or Early Termination. Vital signs include systolic and diastolic blood pressure (SBP and DBP), heart rate (HR), respiration rate (RR) and body temperature. Weight will also be summarized per its collection schedule at Screening, Baseline, Week 12, and Week 24 (End of Study) or Early Termination. Vital signs will be summarized as absolute values and change from baseline using standard summary statistics.

#### **3.8.4.4 Physical Examination**

Physical examinations will be presented at Screening, Baseline, Week 12, and Week 24 (End of Study) or Early Termination. Physical examinations include assessments of general appearance, skin, HEENT (head, ears, eyes, nose and throat), chest and lungs, cardiovascular, abdomen, musculoskeletal and extremities, neurological, psychiatric and mental status.

Knee examinations will be done at Screening, Baseline, Week 2, Week 4, Week 8, Week 12, Week 18, and Week 24 (End of Study) or Early Termination. Knee examinations will be done for both knees at Screening and only for the Index Knee for subsequent visits. Knee examinations include range of motion, presence of an effusion (stroke test), crepitus on palpation with range of motion, stability of collateral ligaments, stability of cruciate ligaments, warmth on palpation of the joint, tenderness on palpation of the joint, gait, and skin appearance.

Both physical examination and knee examination parameters will be listed for each subject and summarized by frequency and percentage, as well as by shift from baseline.

### **3.9 Analysis of Plasma Pharmacokinetic Concentrations**

The pharmacokinetics of EP-104IAR will be assessed by analysis of plasma levels of fluticasone propionate (FP). Blood samples for determination of FP plasma concentrations will be collected at following time points relative to study drug administration: Pre-Dose, 2 hours Post-Dose, Week 1, Week 2, Week 4, Week 8, Week 12, Week 18 and Week 24 (End of Study). PK data will be analyzed using the Safety Population.

Where estimable, the following plasma PK parameters calculated for FP will be calculated using non-compartmental methods:

- the maximum quantifiable plasma concentration ( $C_{max}$ )
- the time to reach maximum quantifiable plasma concentration ( $t_{max}$ )

	EP-104IAR-201 Statistical Analysis Plan	Version: Final 1.0
	Date: 14-Jun-2023	Page 28 of 38

- the last quantifiable plasma concentration ( $C_{last}$ )
- the time to reach the last quantifiable plasma concentration ( $t_{last}$ )
- the terminal disposition rate constant ( $\lambda_z$ ) with the respective half-life ( $t_{1/2}$ )
- the area under the concentration-time curve from time zero to the time of last quantifiable concentration ( $AUC_{0-t}$ )
- the area under the concentration-time curve from zero to infinity ( $AUC_{0-\infty}$ )
- the area under the concentration-time curve from time zero to 24 weeks post-dose ( $AUC_{0-24wks}$ )
- the percentage of the area under the concentration-time curve extrapolated to infinity ( $AUC\%_{extrap}$ )
- the apparent clearance (CL/F)
- the apparent volume of distribution ( $V_z/F$ ).

The individual PK parameters of FP will be presented in data listings and summarized for subjects receiving EP-104IAR using descriptive statistics (number of subjects, mean, SD, geometric mean, geometric mean CV, median, Q1, Q3, minimum, and maximum). Geometric mean versus nominal time profiles will be presented in figures on both linear and semi-logarithmic scales (base 10). Concentration values that are BLQ of the assay will be treated as half the LLOQ when calculating summary statistics for plasma concentrations. Where all values are BLQ, the mean, geometric mean, median, minimum, and maximum concentration will be presented as BLQ and the SD will be reported as not applicable. Concentration values reported as BLQ will be listed with the LLOQ in parentheses. Missing values will not be imputed when calculating summary statistics for plasma drug concentrations and for calculating PK parameters.

For the derivation of PK parameters, pre-dose plasma concentration results will be analyzed as time 0 (hours post-dose) and all post-dose plasma concentration results will be analyzed according to their actual sampling times relative to dosing. Concentration data will be used as received from the bioanalytical laboratory without rounding.

Residual EP-104IAR in used injection kits will be used to calculate actual doses received. From this, dose proportionality for PK parameters (AUC and  $C_{max}$ ) will be assessed using the power model:  $P = \beta_0 \times Dose^{\beta_1}$ , where P represents the parameter result. The natural log of the power model will be used to fit the data using an analysis of variance with effect dose:  $\ln(P) = \ln(\beta_0) + \beta_1 \times \ln(dose)$ . An estimate of  $\beta_1=1$  would indicate perfect dose proportionality. The slope parameter  $\beta_1$  and its associated confidence interval will be estimated and summarized. Additionally, the PK parameter (AUC and  $C_{max}$ ) multiplication factor associated with a 2-fold

	EP-104IAR-201 Statistical Analysis Plan	Version: Final 1.0
	Date: 14-Jun-2023	Page 29 of 38

increase in dose along with its corresponding confidence interval will be included in summary table. The multiplication factor and associated confidence interval will be estimated as  $2^{\beta_1}$  and  $(2^{\text{lower confidence limit of } \beta_1}, 2^{\text{upper confidence limit of } \beta_1})$ , respectively.

PK parameters will be derived as follows. PK parameters containing a time component for their unit of measure are presented below using hours (h). However, a different unit of time (e.g., days, weeks) may be utilized instead depending on the scale of the parameter.

